4.5.1.1. Selection of 3 mg/day

The dosing recommendation for the investigation of brain contusion is guided by the clinical experience of BIIB093 in healthy volunteers and patients with LHI. Briefly, the IV infusion regimen for LHI in Phase 3 was refined based on dose escalation results from the Phase 1 study (Study 101: first-in-human study in healthy volunteers) and PK modeling, encompassing a 3stage IV infusion regimen (IV bolus followed by 2 infusion periods). The 3 mg/day dose was the highest dose tested in Study 101 in which severe hypoglycemia was not observed, and it had an acceptable safety profile and was well tolerated in the LHI Phase 2 studies. Additionally, this dosing regimen is selected to rapidly achieve and maintain the desired systemic steady-state concentration (approximately 25 ng/mL) of BIIB093 previously shown to be efficacious in patients with LHI. Efficacy of BIIB093 at 3 mg/day in brain contusion is also anticipated based on the similar pathophysiology between LHI and brain contusion. This is also supported by preclinical evidence (rat models of brain contusion), which demonstrated that glibenclamide significantly reduced progressive secondary hemorrhage with a dosing regimen identical to that used in LHI animal models [Simard 2010].

CONFIDENTIAL

The information contained herein may not be used, disclosed, or published without the written consent of Biogen MA Inc.

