¹⁰ The optional blood sample for pharmacogenetic analysis requires a separate informed consent form to be administered between the start of study and hospital discharge. The pharmacogenetic sample should be collected as close to the consenting procedure as possible and preferably within 24 hours of the start of study treatment. The date and time of collection should be recorded.

¹¹ A delayed intubation eCRF must be completed if a participant is intubated for deteriorating neurologic status.

¹² Hourly (\pm 30 minutes) for Hour 0 to Hour 24, every 2 hours (\pm 30 minutes) for Hour 25 to Hour 48, and every 4 hours (\pm 60 minutes) for Hour 49 to Hour 96. If treatment for low BG (< 70 mg/dL [\sim 3.9 mmol/L]) is initiated, then BG monitoring is required every 15 minutes (\pm 10 minutes) until BG is \geq 80 mg/dL (\sim 4.4 mmol/L) for 3 consecutive readings without exogenous bolus glucose supplementation. See Section 11.4.1.1.1 for details on BG monitoring and management.

¹³ [REDACTED] A CMO eCRF must be completed for participants for whom care is withdrawn.

¹⁴ An NCCT scan is sufficient for participants who cannot get an MRI.

¹⁵ The 96 hour scan should be performed after study treatment infusion is complete, within 18 hours of the Hour 96 time point.

¹⁶ Only required if ET occurs before the Hour 96 scan has been performed.

¹⁷ Includes all AEs from the beginning of study treatment administration and all SAEs from the time of consent. AEs of special interest (hypoglycemia [BG < 55 mg/dL (\sim 3.1 mmol/L)]) will be upgraded to an SAE. See Section 15.3 for further details on monitoring and recording AEs.

¹⁸ A short suicidal ideation/behavior questionnaire will be conducted on participants who are alert and capable of providing answers at Screening (prior to dosing). For these participants, this questionnaire should be repeated at Days 30, 90, 180, and ET Visit. The questionnaire conducted at Screening will record “Life Time” events and subsequent visits (at Days 30, 90, 180, and ET Visit) will record “Since the Last Visit” events.

CONFIDENTIAL

The information contained herein may not be used, disclosed, or published without the written consent of Biogen MA Inc.

Table 3: ECG, [REDACTED] Schedule of Activities

	12-lead ECG¹	
Predose	SOC ECG taken at Screening	
Minute 5	±5 minutes	
Hour 6	±5 minutes	
Hour 24	±5 minutes	
Hour 48	±5 minutes	
Hour 72	±5 minutes	
Hour 96	±5 minutes	

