7. STUDY DESIGN

7.1. Study Overview

This is a Phase 2, randomized, multicenter, double-blind, multidose, placebo-controlled study to assess the efficacy and safety of BIIB093 in inhibiting the progression of traumatic intracerebral contusions in participants aged 18 to 85 years.

Approximately 60 sites in 7 countries globally are planned. The study will randomize 160 participants.

Participants must be treated with BIIB093 within 10 hours of time of trauma/LKN and within 6 hours of hospital arrival. Dosing should be initiated within 1 hour of randomization and continue for 96 hours (4 days). For participants in the 3 mg/day dose arm, treatment will be initiated similarly to the regimen in an ongoing Phase 3 study targeting edema associated with LHI. Participants will receive a bolus IV dose of 0.13 mg (given over approximately 2 minutes), followed by 2 different infusion rates (a rapid IV infusion of 0.1644 mg/h for 6 hours followed by a slow IV infusion of 0.1134 mg/h for the remaining 90 hours). In the 5 mg/day dose arm, participants will receive a bolus IV dose of 0.21 mg (given over approximately 2 minutes), followed by 2 different infusion rates (a rapid IV infusion of 0.2722 mg/h for 6 hours followed by a slow IV infusion of 0.1871 mg/h for the remaining 90 hours). These treatment rates should be administered within the limitation of the device at the site. The treatment duration will be for 96 hours for both treatment groups.

The primary endpoint of this study will be the change in total contusion volume (hematoma plus perihematomal edema) as measured by brain imaging from baseline to 96 hours, or prior to DC, IPH evacuation, or CMO, if these procedures occur before 96 hours.

[figure not shown]
Participants will also have the functional assessments (i.e., GOS-E, [REDACTED], and mRS) performed at both Day 90 and Day 180 post trauma.

After the last participant completes their Day 4 (Hour 96) Visit, data for the primary endpoint and available data for the secondary endpoints will be locked for analysis. The final database lock will occur after the last participant completes their Day 180 Follow-up Visit, marking the end of the study.

See Figure 1 for a schematic of the study design.

CONFIDENTIAL

The information contained herein may not be used, disclosed, or published without the written consent of Biogen MA Inc.

Figure 1: Study Design

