**Table 1. Visit Windows for Efficacy Endpoints**

Volume Data		
Analysis visit	Target timepoint in hr	Analysis visit window
Screening	0	Most recent non-missing pre-dose value
Hour 24	24	[10, 38]
Hour 96	96	[76, 116]
GOS-E		
Analysis visit	Target visit day	Analysis visit window
Hospital discharge	7	(0, 23)
Day 30	30	[23, 60]
Day 90	90	(60, 135)

Day 180	180	$\geq 135$
mRS, [REDACTED] [REDACTED]		
Analysis visit	Target visit day	Analysis visit window
Day 90	90	(45, 135)
Day 180	180	$\geq 135$
GCS		
Analysis visit	Target timepoint in hour	Analysis visit window
Screening	0	Most recent non-missing pre-dose value
Hour 24	24	(12, 36]
Hour 48	48	(36, 60]
Hour 96	96	(84, 120]

Study visits and associated visit windows for all remaining analyses are specified in [Table 2](#), which are subject to change prior to the Day 4 administrative database lock. Study period in the table is defined in [Section 3.3](#). Detailed protocol-specified schedule of activities and study visits in Table 2 of the protocol are attached in [Appendix 1](#).

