## **3.3. Study Periods**

### **Pretreatment Period**

The pretreatment period begins at the admission to hospital at the screening visit until start time of study drug infusion (Hour 0).

Measurements taken before the time of study drug infusion at Hour 0 are considered pretreatment for all data domains. If the time of measurement is missing, measurements taken on

Day 1 are considered pretreatment for the following data domains: demography, disease history, ECG, human genotyping, laboratory test results, medical history, physical examinations, participant status, and vital signs.

Baseline value is defined as the last non-missing value before the time of study drug infusion (Hour 0) or prior to or on Day 1 if the time of study drug infusion is missing.

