#### **5.7.5 Electrocardiogram (ECG)**

The number (%) of participants with shifts to categorical values (abnormal not AE, or abnormal AE) will be summarized by actual treatment group. ECG parameters include heart rate, PR Interval, RR Interval, QRS Duration, QT Interval, QTcF, and QTcB, where QTcB is calculated as QT/(RR/1000)1/2. The actual values and change from baseline for each of the ECG parameters will be summarized by actual treatment group and by visit summary. If there are multiple records fall into the same visit windows, the worst record will be presented in the summary.

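### The Minute 5 and Hour 6 ECGs share one 0-12 h window and only the worst is summarised, which biases the within-arm change at that visit upward and merges two differently timed readings

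*SAP*

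**What the plan says.** Table 3 of the protocol (repeated in SAP Appendix 2) lists a pre-dose tracing, "SOC ECG taken at Screening", and post-dose ECGs at Minute 5, Hour 6, Hour 24, Hour 48, Hour 72 and Hour 96, each with a tolerance of ±5 minutes. The early times follow the infusion stages. In the 3 mg/day arm, Protocol 7.1 describes, after the bolus, "a rapid IV infusion of 0.1644 mg/h for 6 hours followed by a slow IV infusion of 0.1134 mg/h for the remaining 90 hours".

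SAP Table 1 covers efficacy endpoints only. For everything else, SAP 3.1 states: "Study visits and associated visit windows for all remaining analyses are specified in" Table 2. The on-treatment windows there are 0-12 h, 12-36 h, 36-60 h, 60-84 h and 84-120 h, followed by an extension. SAP 3.1 also says of these windows: "which are subject to change prior to the Day 4 administrative database lock".

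SAP 5.7.5 plans categorical shift counts and, for the numeric parameters: "The actual values and change from baseline for each of the ECG parameters will be summarized by actual treatment group and by visit summary". It then adds: "If there are multiple records fall into the same visit windows, the worst record will be presented in the summary". The rule in SAP 3.1 that picks the assessment closest to target is written for efficacy data and does not reach ECGs. Under SAP 3.3, baseline is the last available value before Hour 0, which is one record not chosen for its severity.

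**The concern.** The overlap comes from the schedule itself. It affects every participant who has both early ECGs, without any unscheduled tracing. The larger of two noisy readings is higher on average than one reading, so a change computed from it against a single baseline is positive even when nothing has happened. A QTc column would then show a rise at Hour 0-12 that falls away at Hour 24, in placebo as well as active arms.

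The merged row also cannot say whether the reading came just after the bolus or at the end of the faster infusion stage. Those are the only two scheduled post-dose ECGs in that part of the regimen.

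The plan treats QT as a safety matter. Exclusion criterion 9 uses QTc > 520 ms, and Protocol 10.1 has a discontinuation criterion at > 550 ms. Protocol 4.5.1.2 says that doses between 3 and 6 mg/day have not been studied clinically and that the 5 mg/day exposures are simulated. ECG is also among the interim safety outputs in SAP 4.1. In the visible text of SAP 5.7.5 the by-visit table is the only numeric ECG output, and no ECG listing is mentioned there.

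**Working it through.** The documents give no figure for this rule, so there is none to reproduce.

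**Step 1: windows.** Minute 5 ± 5 minutes runs from 0 to 10 minutes, or 0 to 0.17 h. Hour 6 ± 5 minutes runs from 5.92 to 6.08 h. Both always lie within 0-12 h. Hours 24, 48, 72 and 96 each fall alone in their own window.

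**Step 2: infusion rate.** The rate up to Hour 6 relative to the later rate is 0.1644/0.1134 = 1.45 in the 3 mg/day arm and 0.2722/0.1871 = 1.45 in the 5 mg/day arm.

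**Step 3: bias with no drug effect.** Take worst to mean the larger value, chosen for each parameter. Let the readings at the two times have the same mean as baseline, normal within-participant errors with SD s, and correlation ρ between the two errors. Then

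E[larger of two] − E[single reading] = s·√((1−ρ)/π), which is s/√π = 0.564·s when ρ = 0.

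**Step 4: effect at one time only.** Let the drug add δ at one of the two times and nothing at the other. With θ = s√2 and d = δ/θ (ρ = 0), the active-arm mean of the larger reading is δ·Φ(d) + θ·φ(d). The placebo mean is s/√π, and the apparent effect is the difference.

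For s = 10 and δ = 10: θ = 14.14 and d = 0.707. The active mean is 10 × 0.760 + 14.14 × 0.311 = 12.0. The placebo mean is 5.64. The difference is about 6.4 ms.

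The documents give no within-participant QTc SD, so s is an assumption shown over a range:

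| Assumed s (ms) | Bias in each arm, ρ = 0 | Bias in each arm, ρ = 0.5 | Apparent effect if a true 10 ms is present at one time only (ρ = 0) |
|---|---|---|---|
| 8 | 4.5 | 3.2 | 6.7 |
| 10 | 5.6 | 4.0 | 6.4 |
| 15 | 8.5 | 6.0 | 5.9 |

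Over a wider range of s = 5 to 20 ms with ρ = 0, the bias runs from 2.8 to 11.3 ms and the apparent effect from 7.4 to 5.7 ms.

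**Step 5: effect at both times.** If δ is present equally at both times, each arm keeps the same s/√π and the difference remains δ, here 10 ms.

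**Step 6: simulation.** With 2,000,000 draws at s = 10, the mean change was 5.64 ms using the larger of two readings and 0.01 ms using one reading. It was 11.99 ms with a 10 ms effect at one time. These agree with the formulas (5.64, 0 and 12.0).

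**The case against.** The strongest reply is that this is a descriptive safety table with no ECG hypothesis test. The selection acts alike in all arms, and it keeps the more adverse reading rather than discarding it. That largely stands. A reader might infer that the rule inflates the drug-placebo difference. With no drug effect and equal numbers of early ECGs per arm, it does not. Dilution needs an effect at one time and not the other.

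A reader might also infer that the rule hides the effect at peak exposure. The documents do not say when concentration peaks. Protocol 4.5.1.1 says only that "this dosing regimen is selected to rapidly achieve and maintain the desired systemic steady-state concentration". What the text supports is that the bolus and the highest infusion rate fall within the first 6 hours. The larger reading survives, but its time label does not.

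It is tempting to add that the Minute 5 tolerance lets a pre-drug tracing count as post-bolus. Hour 0 is the start of study treatment and the bolus is its first stage, so a tracing in the first 2 minutes is taken during the bolus, not before it.

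The size depends on what worst means. If the record is chosen by its overall grade (abnormal not AE, abnormal AE) rather than parameter by parameter, s/√π does not apply. The objection is fair to the figures, but it also shows that the rule is open to more than one implementation.

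Finally, Table 2 may still change before the Day 4 lock, and redacted SAP sections may contain a time-matched ECG analysis. The first allows the correction without making it. The second means that one cannot say that no such analysis exists, only that SAP 5.7.5 does not provide it.

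**Conclusion.** The point holds within limits. As written, SAP Table 2 and SAP 5.7.5 merge the two early ECGs and summarise only the worst. For parameters where worst is the largest value, within-arm mean change at Hour 0-12 is biased upward by about 4.5 to 8.5 ms for assumed SDs of 8 to 15 ms with independent errors, or 3.2 to 6.0 ms at a correlation of 0.5. The between-arm comparison is unaffected when there is no effect, or when the effect is the same at both times, provided the arms have equal numbers of ECGs. A 10 ms effect at one time only would appear as about 6.7 to 5.9 ms, with its timing lost from the by-visit table. These figures rest on the assumed SDs, normal errors and a per-parameter maximum. Separately, and without any assumption, worst has no stated direction for heart rate, PR or RR. The issue is confined to the 0-12 h row unless unscheduled or repeat ECGs add records elsewhere, and it does not touch the efficacy analyses.

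**What to change.** In SAP 5.7.5, base the by-visit summaries of values and changes on the nominal times in Protocol Table 3, with Minute 5 and Hour 6 as separate analysis visits followed by Hours 24, 48, 72 and 96. Where a visit has several records, use the one closest to nominal time. Keep the worst post-baseline record for the categorical shift summary only. Define worst for each parameter, giving both directions where either can be abnormal, and say whether it is chosen by parameter or by tracing.

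Under the assumptions above, one record per visit removes the selection bias, and a 10 ms effect at one time is estimated as 10 ms at that time. The cost is SAP wording and one extra column in the ECG tables. No new assessment is needed, and the change can be made before the Day 4 lock.

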#### **5.7.6 Vital Signs**

Vital signs measures include oxygen saturation, heart rate (pulse), respiratory rate, temperature, and systolic and diastolic blood pressure. The analysis of vital signs will focus on the incidence of clinically relevant abnormalities for participants in safety analysis set. The abnormalities for temperature, heart rate, systolic blood pressure, and diastolic blood pressure are provided in Table 6 of the protocol.

- The number of participants evaluated and the number (%) of participants with clinically relevant post-baseline abnormalities will be presented by actual treatment group.
- Summary statistics for actual values and change from baseline will also be presented by actual treatment group.
- Participant listing of vital signs will be provided.

A 2D grayscale heatmap showing a distribution of data points. The x-axis represents 'X' and the y-axis represents 'Y'. The distribution is highly concentrated in a central region, with a significant tail extending towards the bottom right. A vertical line is drawn at X=100, and a horizontal line is drawn at Y=100. The distribution is roughly bounded by X=50 to 150 and Y=50 to 150.

### 5.10. <Additional> Patient Reported Outcomes (PROs)

Not applicable

### 5.11. <e.g., Antigenicity/Immunogenicity> Endpoints

Not applicable

## 5.12. <Other Analyses>

Not applicable

### 5.13. Statistical Considerations for Interim Analysis

The interim analysis will not inform the continued blinded data collection in the study. There is no Type I error adjustment for the interim analysis. The analysis of the primary and available data for the secondary endpoints will be performed after the last participant completes the Day 4 (Hour 96) Visit.

## 6. Changes from Protocol-Specified Analyses

Not applicable for this version.

## 7. Summary of Changes from the Previous Version of the SAP

Not applicable for this version.

## **APPENDICES**

## APPENDIX 1. IMAGING DATA PER THE CENTRAL REVIEW

### *On-Protocol Images for the Central Review*

MR and NCCT images will be used to assess changes in brain contusion, hemorrhage and edema volume, [REDACTED]. Eligible participants will undergo NCCT at baseline and Hour 24 and MRI/NCCT at Hour 96.

- Screening NCCT will be the one closest to the randomization, which is assessed for eligibility with a brain contusion volume of > 3mL per investigator review and used for stratification at randomization
- All NCCT/MRI brain images collected by the imaging CRO up to the Hour 96 visit (or NSx or CMO, if earlier) will be considered on-protocol images and will be submitted for central review

### *Imaging Data per the Central Review*

Key reading process and imaging data per the central review will be provided as follows:

- Image quality control (QC) personnel will review all received imaging data to ensure accuracy of labeling and appropriateness for reads of all on-protocol imaging
- Two independent neuroradiologist readers trained on the study will read each participant case once all on-protocol images are available. Initial reads (i.e., 2 records per image) will be locked and provided for all available time points
- Following completion of initial reading, a single final read per participant-time point is determined through averaging of the two independent reads or by reader consensus per procedure outlined in the brain MRI/NCCT worksheet (BMCW) Completion Guidelines version 2.0

## APPENDIX 2. SCHEDULE OF ACTIVITIES

The schedule of activities is described in Section 5 of the protocol.

**Table 3: Schedule of Activities**

	Screening/ Enrollment	Hours 0-12 	Hour 24 (±6 h)	Hour 48 (±12 h)	Hour 72 (±12 h)	Hour 96 (±12 h) 	Day 7 (±24 h) 	Hospital Discharge (±24 h) 	Day 30 (±7 d) 	Day 90 (±14 d) 	Day 180 (±14 d) 	NSx/Comfort Measures (if applicable)	ET Visit
Inclusion/ exclusion criteria	X												
Informed consent	X												
Demographics, medical history, physical examination (including weight and height)	X												
TT/LKN	X												
NCCT 	X 		X			X 						X	
GCS	X		X	X		X							
Pregnancy test (urine or serum)	X												
Blood alcohol level	X												
Blood sampling for coagulation panel (INR, PTT, fibrinogen)	X												
Blood sampling for hematology and blood chemistry	X						X						X 
Blood sampling for LFTs	X		X	X	X	X	X						
Vital signs 	X	X	X	X	X	X	X						X

	Screening/ Enrollment	Hours 0-12 	Hour 24 (±6 h)	Hour 48 (±12 h)	Hour 72 (±12 h)	Hour 96 (±12 h) 	Day 7 (±24 h) 	Hospital Discharge (±24 h) 	Day 30 (±7 d) 	Day 90 (±14 d) 	Day 180 (±14 d) 	NSx/Comfort Measures (if applicable)	ET Visit
Other assessments (ECG, [REDACTED])													
Blood sampling for pharmacogenetics (optional) 													
Enrollment/randomization (TT/LKN < 10 h)	X												
Study treatment (TT/LKN < 10 h)			← 96-hour infusion → (see Protocol Section 4.5.1 for further details)										
Delayed intubation eCRF 			X	X	X	X							
BG measurement 	X	X	X	X	X	X	X						
Concomitant therapy	X	X	X	X	X	X	X	X	X	X	X	X	X
Concomitant procedures 	X	X	X	X	X	X	X	X	X	X	X	X	X
Craniectomy/comfort care/ cranioplasty assessment form(s)												X	
MRI 						X 						X	X 
GOS-E									X	X	X	X	X
mRS										X	X		X
Review safety data and record AEs/SAEs 	X	X	X	X	X	X	X	X	X	X	X		X

	Screening/ Enrollment	Hours 0-12 	Hour 24 (±6 h)	Hour 48 (±12 h)	Hour 72 (±12 h)	Hour 96 (±12 h) 	Day 7 (±24 h) 	Hospital Discharge (±24 h) 	Day 30 (±7 d) 	Day 90 (±14 d) 	Day 180 (±14 d) 	NSx/Comfort Measures (if applicable)	ET Visit
Brief suicide ideation/behavior assessment 	X								X	X	X		X

AE = adverse event; BG = blood glucose; CMO = comfort measures only; d = days; DC = decompressive craniectomy; ECG = electrocardiogram; eCRF = electronic case report form; ET = early termination; [REDACTED]; GCS = Glasgow Coma Scale; GOS-E = Glasgow Coma Scale-Extended; h = hours; INR = international normalized ratio; IPH = intraparenchymal hematoma; LFT = liver function test; LKN = last known normal; MRI = magnetic resonance imaging; mRS = modified Rankin Scale; NCCT = noncontrast computed tomography; NSx = neurosurgical intervention; [REDACTED]; PTT = partial thromboplastin time; [REDACTED]; SAE = serious adverse event; SOC = standard of care; TT = time of trauma.

 Hour 0 is defined as the start of study treatment infusion.

 In the event a participant is discharged from the hospital prior to Hour 96, every effort should be made to obtain neuroimaging (NCCT or MRI) prior to discharge.

 If a participant is due to be discharged from hospital prior to Day 7, every effort should be made to perform the Day 7 assessments at the time of discharge or just prior.

 All visits after hospital discharge can be conducted by telephone; however, the Day 90 and Day 180 Visits should be in person whenever possible. Should the follow-up visits at Day 90 and Day 180 be conducted remotely, [REDACTED].

 Scans (NCCT or MRI) obtained within 12 hours of IPH evacuation, DC, or CMO meet the requirement. Scans are not expected for other NSx interventions. If IPH evacuation, DC, or CMO are indicated prior to 96 hours, an NCCT or MRI scan in the 12 hours proceeding the procedure should be collected, and no further post procedural images are required beyond SOC.

 NCCT as SOC at Screening (prior to enrollment). If not eligible per SOC scan, a single, repeat, study-specific NCCT may be obtained to reassess contusion volume if feasible within the protocol-specified time window.

 Optional Hour 96 NCCT should be obtained in addition to the MRI whenever possible, after study treatment infusion is complete, within 18 hours of the Hour 96 timepoint.

 Only performed if participant has not yet been discharged from hospital.

 Vital signs include temperature, pulse rate, systolic and diastolic blood pressure, respiratory rate, and oxygen saturation. Measurements taken nearest to the assessment timepoint should be recorded.

The optional blood sample for pharmacogenetic analysis requires a separate informed consent form to be administered between the start of study and hospital discharge. The pharmacogenetic sample should be collected as close to the consenting procedure as possible and preferably within 24 hours of the start of study treatment. The date and time of collection should be recorded.

A delayed intubation eCRF must be completed if a participant is intubated for deteriorating neurologic status.

Hourly ( $\pm$ 30 minutes) for Hour 0 to Hour 24, every 2 hours ( $\pm$ 30 minutes) for Hour 25 to Hour 48, and every 4 hours ( $\pm$ 60 minutes) for Hour 49 to Hour 96. If treatment for low BG (< 70 mg/dL [ $\sim$ 3.9 mmol/L]) is initiated, then BG monitoring is required every 15 minutes ( $\pm$ 10 minutes) until BG is  $\geq$  80 mg/dL ( $\sim$ 4.4 mmol/L) for 3 consecutive readings without exogenous bolus glucose supplementation. See Protocol Section 11.4.1.1.1 for details on BG monitoring and management.

██████████ A CMO eCRF must be completed for participants for whom care is withdrawn.

An NCCT scan is sufficient for participants who cannot get an MRI.

The 96 hour scan should be performed after study treatment infusion is complete, within 18 hours of the Hour 96 time point.

Only required if ET occurs before the Hour 96 scan has been performed.

Includes all AEs from the beginning of study treatment administration and all SAEs from the time of consent. AEs of special interest (hypoglycemia [BG < 55 mg/dL ( $\sim$ 3.1 mmol/L)]) will be upgraded to an SAE. See Protocol Section 15.3 for further details on monitoring and recording AEs.

A short suicidal ideation/behavior questionnaire will be conducted on participants who are alert and capable of providing answers at Screening (prior to dosing). For these participants, this questionnaire should be repeated at Days 30, 90, 180, and ET Visit. The questionnaire conducted at Screening will record “Life Time” events and subsequent visits (at Days 30, 90, 180, and ET Visit) will record “Since the Last Visit” events.

